5.9 Subject Withdrawal/Discontinuation Criteria

Subjects may withdraw consent at any time for any reason or be discontinued from the trial at the discretion of the Investigator should any untoward effect occur. In addition, a subject may be withdrawn by the Investigator or the Sponsor if enrollment into the trial is inappropriate, the trial plan is violated, or for administrative and/or other safety reasons. Specific details regarding discontinuation or withdrawal are provided in [Section 7.1.4](#).

Subjects may be discontinued from the trial for any of the following reasons:

- The subject withdraws consent
- Documented disease progression (radiographic and/or clinical)
- Unacceptable adverse experiences as described in [Section 5.2.1.2](#)
- Death
- Investigator's decision to withdraw the subject
- Noncompliance with trial treatment or procedure requirements
- The subject is lost to follow-up
- Completed 24 months of study treatment with ADXS31-142/pembrolizumab (MK-3475). **Note:** 24 months of study medication is calculated from the date of first dose.
- Achieved irCR (complete response)
- Randomized/Registered but never received study drug
- Study terminated by Sponsor
- Other (specify)

The End of Treatment and Follow-up visit procedures are listed in [Section 6](#) and [Section 7.1.5](#). After the end of treatment, each subject will be followed for AE/SAE monitoring as described in [Section 7.2.3.1](#). In addition to the *Lm* Surveillance Monitoring, subjects who discontinue for reasons other than progressive disease will have post-treatment follow-up (████████ every 4 weeks and imaging every 12 weeks) until disease progression, initiating an anti-cancer therapy, withdrawing consent, becoming lost to follow-up, or the Sponsor ends the study.

5.10 Subject Replacement Strategy

Subjects will not be replaced.

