5.2.1.1.1 Dose Limiting Toxicity Criteria

The same DLT criteria will be utilized for study Part A and Part B. All toxicities will be graded using CTCAE v 4.03. The DLT window of observation will begin at the administration of the initial dose of ADXS31-142 and end 1 week following the second dose of ADXS31-142. The occurrence of any of the following toxicities will be considered a DLT, if judged by the investigator to be possibly, probably or definitely related to study treatment administration. Treatment modifications for DLT are shown in Table 8 and Table 9.

General:

1. Prolonged delay (>2 weeks) in initiating the second dose due to treatment-related toxicity
2. Missing the second dose of ADXS31-142 or pembrolizumab (MK-3475) as a result of AE(s) during the first cycle.

Hematologic:

1. Grade 4 hematologic toxicity.
2. Febrile neutropenia, defined as absolute neutrophil count (ANC) $< 1000/\text{mm}^3$ with a single temperature of >38.3 degrees C (101 degrees F) or a sustained temperature of ≥ 38 degrees C (100.4 degrees F) for more than 1 hour.
3. Grade 3 thrombocytopenia lasting >72 hours.
4. Grade 4 thrombocytopenia.

Non-Hematologic:

1. \geq Grade 3 non-hematologic toxicity, (excluding nausea, vomiting and/or diarrhea lasting <3 days and reversible with medical intervention).
2. Grade 3 non-hematologic laboratory value that does not downgrade to Grade 2 within 3 days after onset of the event despite optimal medical management (excluding transient Grade 3 laboratory value abnormalities reversible within 5 days and without medical intervention).
3. Listeremia: positive blood culture(s) along with persistent (for 72 hours post dose) symptoms consistent with listeremia (e.g., fever and muscle aches, often preceded by diarrhea or other gastrointestinal symptoms).
4. \geq Grade 3 flu-like or cytokine release symptoms that persist for >24 hours after ADXS31-142 administration despite symptomatic treatment (Refer to Section 7.2.3.2).

Subjects who experience a DLT at Dose Level -1 of 0.5×10^9 will be discontinued from study treatment. However, subjects who experience a DLT at DL 1 of 1×10^9 may be eligible to receive ADXS31-142 at a lower dose level for subsequent doses and cycles following discussion and agreement between the Investigator and Sponsor.

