5.2.1.1.3 Part B – ADXS31-142 + Pembrolizumab (MK-3475) Combination Therapy

Part B consists of a modified 3+3 design to identify a recommended RP2D of the combination which will be used in the Part B expansion phase. The starting ADXS31-142 dose for Part B will be the RP2D determined in Part A. For example, if 1×10^9 cfu is determined to be the RP2D in Part A then that will be the starting dose. The ADXS31-142 dose will not be escalated in Part B. However, if the ADXS31-142 dose of 1×10^9 cfu (Dose Level 1) isn't tolerable in combination, then the dose of ADXS31-142 will be de-escalated to a dose of 0.5×10^9 cfu (Dose Level -1) in combination with pembrolizumab (MK-3475) 200 mg.

Interim safety data review and/or DLTs observed at the first dose level will be used to determine the need for de-escalation to the next lower dose level. Determination to dose de-escalate will be made according to a modified 3+3 design as follows:

An initial cohort of 3 subjects will be enrolled at doses of ADXS31-142 1×10^9 cfu in combination with pembrolizumab (MK-3475) 200 mg.

- If 0/3 subjects develop a DLT,
 - Another 3 subjects will be enrolled at this dose level.
 - If 0, 1 or 2 of the 3 new subjects develops a DLT (for a total of 0/6, 1/6 or 2/6 subjects with a DLT at this dose level), the current dose will be considered the RP2D and the trial will proceed to the dose expansion stage.
 - If 3 of the 3 new subjects develop a DLT (for a total of 3/6 subjects with a DLT at this dose level), the dose will be de-escalated to DL -1 and a dose of ADXS31-142 0.5×10^9 will be administered in combination with pembrolizumab (MK-3475) 200 mg.
- If 1/3 subjects develop a DLT,
 - Another 3 subjects will be enrolled at this dose level.
 - If 0 or 1 of the 3 new subjects develops a DLT (for a total of 1/6 or 2/6 subjects with a DLT at this dose level), the current dose will be considered

the recommended MTD, and the trial will proceed to the dose expansion stage.

- If >1 of the 3 new subjects develop a DLT (for a total of >2/6 subjects with a DLT at this dose level), the dose will be de-escalated to DL -1 of ADXS31-142 0.5×10^9 in combination with pembrolizumab (MK-3475) 200 mg.
- If 2/3 or 3/3 subjects develops a DLT the dose will be de-escalated.

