If, following the rules above the dose is de-escalated, the 3 + 3 rules above will be repeated. Should additional de-escalation be required, a dose lower than 0.5×10^9 may be considered or the Sponsor may decide to take other action (e.g., stop the trial) based on a comprehensive review of the data from this trial as well as other trials.

This protocol will also allow de-escalation to an intermediate, not pre-defined and not previously-studied dose, if evaluation of toxicity at such a dose is desired in lieu of proceeding directly to the dose expansion stage of the trial.

Table 7 ADXS31-142 and Pembrolizumab (MK-3475) Combination Therapy Doses to be used in Trial Part B

Drug	Dose Level	Dose	Route of Administration	Regimen
ADXS31-142	11	1×10^9	IV infusion	Day 1 of Weeks 1, 4 and 7 of 12-week cycle
	-1	0.5×10^9	IV infusion	Day 1 of Weeks 1, 4 and 7 of 12-week cycle
Pembrolizumab (MK-3475)		200 mg	IV infusion	Day 1 Q3W of 12-week cycle

Cohort Expansion: Once the RP2D is decided, an additional cohort of subjects will be enrolled at the selected RP2D for combination therapy. The number of subjects will depend on the number of subjects previously treated in the dose-finding portion. It is planned to treat a total of approximately 30 subjects at the RP2D. Subjects will be enrolled on a rolling basis.

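### Part B has no rule for a subject who leaves the DLT window early for a non-toxicity reason, so the RP2D can rest on fewer than 6 DLT-evaluable subjects

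*Combined protocol and SAP*

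**What the plan says.** - **Replacement (5.10).** The whole section reads "Subjects will not be replaced".
- **DLT window (5.2.1.1.1).** "The DLT window of observation will begin at the administration of the initial dose of ADXS31-142 and end 1 week following the second dose". Table 7 schedules ADXS31-142 on "Day 1 of Weeks 1, 4 and 7 of 12-week cycle".
- **Toxicity-driven loss of dose 2 (5.2.1.1.1).** Two general criteria make this a DLT: "Prolonged delay (>2 weeks) in initiating the second dose due to treatment-related toxicity" and "Missing the second dose of ADXS31-142 or pembrolizumab (MK-3475) as a result of AE(s) during the first cycle". Like all DLTs, they require at least a possible relation to treatment.
- **Decision rule (5.2.1.1.3).** The first cohort is judged on 0/3, 1/3, 2/3 or 3/3. After 0/3 the dose becomes the RP2D "for a total of 0/6, 1/6 or 2/6 subjects with a DLT at this dose level"; after 1/3 it is accepted at 1/6 or 2/6. No other denominator appears.
- **Minimum at the RP2D.** Section 2.1.2 states it as 6 subjects treated, and Section 5.2.1.1 (below Table 5) as at least 6 enrolled. Neither says evaluable for DLT.
- **Analysis sets (8.2.1).** A safety population and an efficacy set are defined, but no DLT-evaluable set. Section 8.2.3 lists DLT among the safety data without a denominator.
- **Exits that are not DLTs (5.9).** These include consent withdrawal, progression, loss to follow-up and noncompliance.
- **Expansion size (5.2.1.1.3).** About 30 subjects in total are planned at the RP2D, and "The number of subjects will depend on the number of subjects previously treated in the dose-finding portion".

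**The concern.** Choosing the RP2D for the combination is a primary objective of Part B, and it turns on six subjects. For a subject who never receives dose 2 for a non-toxicity reason, the window has no defined end. The plan does not say whether that subject counts, and Section 5.10 removes the usual remedy of enrolling another.

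If the subject is dropped, the count is out of 2 or out of 5, for which Section 5.2.1.1.3 has no branch. If the subject is kept, an incomplete observation is read as a tolerated one, which tilts the decision toward accepting the dose. About 24 further subjects (30 − 6) would then be treated at that dose.

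The gap matters for Part B only. Part A is described as completed (5.2.1.1.2), and its Table 5 gives a decision for any number of subjects from 1 to 21.

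**Working it through.** **Length of the window.** Day 1 of Week 1 to Day 1 of Week 4 is 21 days. Adding 7 days after dose 2 gives 28 days, about 4 weeks.

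**The plan's own rule.** Let *p* be the true DLT rate and let each cohort of 3 be binomial. The dose is accepted if the first cohort has 0 DLTs and the second at most 2, or if the first has 1 and the second at most 1:

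P(accept) = P(0 of 3) × P(≤2 of 3) + P(1 of 3) × P(≤1 of 3)

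The accepting paths give totals of 0, 1 or 2 out of 6, as the protocol states. With six fully observed subjects:
- *p* = 40%: 0.216 × 0.936 + 0.432 × 0.648 = 0.202 + 0.280 = 0.482
- *p* = 50%: 0.125 × 0.875 + 0.375 × 0.500 = 0.109 + 0.188 = 0.297
- *p* = 25%, by the same formula: 0.771

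**With early leavers scored DLT-free.** Let *d* be the share leaving before the window ends for a non-toxicity reason with no DLT. The documents give no value, so 5%, 10% and 20% are assumptions. If a leaver loses all chance of contributing a DLT, and leaving is unrelated to DLT risk, *p* becomes *p*(1 − *d*). For example, at *p* = 40% and *d* = 10% the working rate is 36%: 0.262 × 0.953 + 0.442 × 0.705 = 0.562.

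| True DLT rate | 6 evaluable | *d* = 5% | *d* = 10% | *d* = 20% |
|---|---|---|---|---|
| 25% | 0.771 | 0.793 | 0.813 | 0.852 |
| 40% | 0.482 | 0.522 | 0.562 | 0.641 |
| 50% | 0.297 | 0.340 | 0.386 | 0.482 |

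These shifts are upper bounds for each *d*, because a DLT seen after dose 1 still counts. If half of a leaver's risk is observed (assumption), *d* is in effect halved. Exits of 10% and 20% then give 0.522 and 0.562 at *p* = 40%.

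**How often it would arise.** P(at least 1 of 6 not evaluable) = 1 − (1 − *d*)^6, which is 26%, 47% and 74% for *d* = 5%, 10% and 20%. P(at least 2 of 6) is 3%, 11% and 34%.

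**What an accepted count can hide.** A recorded 2/6 (33%) is 2/5 (40%) with one early leaver and 2/4 (50%) with two. A recorded 0/6 has a one-sided 95% upper bound of 39%; for 0/5 it is 45% and for 0/4 it is 53%.

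**Comparison with Table 5.** Table 5 (Part A, 25% target, both epsilons 0.05) reads 2/4 as de-escalate. This checks, assuming a uniform prior. The posterior is Beta(3,3), with 0.058 below 0.20, 0.105 between 0.20 and 0.30, and 0.837 above 0.30. Dividing by the interval widths 0.2, 0.1 and 0.7 gives 0.29, 1.05 and 1.20, and the largest is the over-dosing interval. Table 5 reads 2/5 and 2/6 as stay, so by that yardstick it takes two early leavers, not one, to change the reading.

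**Cost of replacement.** Enrolment for 6 evaluable is 6/(1 − *d*): 6/0.95 = 6.3 and 6/0.90 = 6.7, so 7; 6/0.80 = 7.5, so 8.

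**The case against.** **The documents do not say that early leavers are DLT-free.** A reader might infer that Section 5.10 by itself forces this scoring. It does not. It bars replacement, and no section says how to score such a subject. Section 5.2.1.1 speaks of subjects being evaluated before dose-escalation decisions, so counting everyone enrolled is not the only reading. That sentence, however, belongs to the Part A text and leaves the term undefined. This objection stands against the stronger reading, but it does not close the gap: the alternative of dropping the subject produces a denominator with no decision attached.

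**Toxicity-related exits are largely covered.** DLTs after dose 1 count, and so does treatment-related loss or long delay of dose 2. Section 4.2.2.1 says reactions typically appear 2 to 4 hours after infusion, so much of the dose 1 risk may be seen before a subject leaves. This stands, and it is why the table above is an upper bound.

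**Early exits may be few.** The first on-treatment scan is at Week 10 (6.2, 7.1.5.2), after the window. Treatment may continue past initial radiographic progression (7.1.2.6.9), and entry requires ECOG 0 or 1. Exit rates of 10 to 20% in about 4 weeks have no support in the documents. At 5%, the shift is only 2 to 4 percentage points for true rates of 25 to 50%.

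**There are later safeguards.** De-escalation may rest on interim safety review as well as DLTs, decisions follow discussion between the sponsor and investigators, and Section 5.11 allows termination for adverse reactions. A reader might infer that nothing could correct a wrong RP2D; that goes too far. But none of these is a numerical rule, and none says how to count the early leaver. The wording of at least 6 enrolled permits a further subject, but no rule triggers one.

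**Conclusion.** The gap is real, and it lies in the primary Part B decision. With replacement barred, decisions given only for x/3 and x/6, and the minimum stated as treated or enrolled, one non-toxicity early leaver without a DLT leaves the choice between no decision and a DLT-free score. The RP2D can therefore be declared on fewer than 6 subjects who completed the window. That conclusion does not depend on any assumed exit rate.

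The size of the bias does. It arises only if early leavers are scored DLT-free. With assumed exits of 5 to 20%, acceptance then rises by at most about 4 to 16 points at a true DLT rate of 40%, and 4 to 19 points at 50%. The lower end is the more plausible, given the timing of the first scan. The documents do not support the stronger claims that the plan prescribes DLT-free scoring or that a large distortion is to be expected.

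**What to change.** Amend Sections 5.10 and 5.2.1.1.3 for Part B dose determination to state that:

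1. A subject who has had no DLT and does not complete the DLT window for a reason other than a DLT is not DLT-evaluable and is replaced. This includes a subject who never receives dose 2 for a non-toxicity reason.
2. The 3s and 6s in the decision rules, and the minimum of 6 at the RP2D in Sections 2.1.2 and 5.2.1.1, refer to DLT-evaluable subjects.
3. A subject with a DLT always counts, whether or not the window was completed.
4. Non-evaluable subjects stay in the safety population.

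Add the DLT-evaluable set to Section 8.2.1 so that DLTs are reported on the same denominator.

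The cost is wording plus about 1 to 2 extra dose-determination subjects. Those treated at the RP2D count toward the planned total of about 30. A numerical pause rule for the expansion is a separate design choice and is not needed here. Extending Table 5 to Part B would import the 25% target of Part A, whereas Part B states no target and accepts 2/6.

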5.11 Clinical Criteria for Early Trial Termination

Early trial termination will be the result of the criteria specified below:

1. Quality or quantity of data recording is inaccurate or incomplete
2. Poor adherence to protocol and regulatory requirements

3. Incidence or severity of adverse drug reaction in this or other studies indicates a potential health hazard to subjects
4. Plans to modify or discontinue the development of the study treatment

In the event of the Sponsor's decision to no longer supply study treatment, ample notification will be provided so that appropriate adjustments to subject treatment can be made.

6 TRIAL FLOW CHART

6.1 Part A Flow Chart – ADXS31-142 Monotherapy

Efficacy Measurements/Correlative Studies											
Tumor Imaging ¹⁰	X							X	X		X

1. Repeating 12-week treatment cycles
2. Week 3, Week 6 and Week 9 visits will be performed during Cycle 1 only. After Cycle 1, these visits are not required.
3. Safety follow-up will be conducted via a telephone call 30 days (\pm 5 days) and 90 days for SAE assessment after the last study treatment to confirm the resolution of any ongoing AEs. In addition, [REDACTED] testing every 4 weeks and imaging every 12 weeks (\pm 1 week) should continue for subjects who discontinue treatment for reasons other than progression (Refer to Section 7.1.5.3.).
4. Prior to conducting screening evaluations. Signing of consent does not start the 28 days screening window.
5. Prior to administering any prophylactic medications, place a “[REDACTED]” [REDACTED] The pre-treatment prophylactic regimen must be administered through a temporary IV and completed at least 30 minutes before each ADXS31-142 infusion.
6. Treatment may be administered [REDACTED] of each scheduled infusion. However, ADXS31-142 should not be administered less than 2 weeks apart without Sponsor approval.
7. All subjects will receive a 7-day course of oral antibiotic therapy starting 72 hours after administration of ADXS31-142. All subjects will also receive an additional 6-month oral antibiotic course to be initiated 72 hours following the last dose of study treatment or upon discontinuation (See Section 7.1.5.3.).
8. AEs and SAEs will be assessed from the time informed consent through the completion of the 30 Day and 90-Day Follow-Up periods.
9. Monitor vital signs (including weight) pre-dose for all infusions. Vital signs (excluding weight) will be monitored every [REDACTED] for the first [REDACTED] following the completion of the ADXS31-142 infusion. Height will be measured at screening only.
10. CT/MRI of the abdomen/pelvis and bone scan. Repeated at Week 10 during first cycle and every 12 weeks (\pm 1 week) during treatment. Evaluation should continue every 12 weeks (\pm 1 week) for subjects who discontinue treatment for reasons other than progression.
11. [REDACTED]
12. [REDACTED]
13. [REDACTED]
14. *Lm* Surveillance Monitoring will include routine monitoring of CBC (excluding LDH), CMP (including CRP, ESR) and blood cultures. Testing will be performed every 3 months (\pm 2 week) for 3 years beginning 3 months after the subject's last dose of study treatment or at time of discontinuation. During the 6-month post-treatment antibiotic period, AEs that occur, which are deemed by the Investigator to be related to *Lm* or antibiotic treatment, along with the concomitant medication(s) used to treat the AE(s), will be recorded on the eCRF.

6.2 Part B Flow Chart – ADXS31-142 Monotherapy + Pembrolizumab (MK-3475) Combination Therapy

Study Procedure	Screening ²	12 Week Treatment Cycle ¹								Follow up		
		Wk 1	Wk 3 ³	Wk 4	Wk 6 ³	Wk 7	Wk 9 ³	Wk 10	Wk 12	End of Therapy procedures	30- & 90-Day Follow-up ⁴	Lm Surveillance Monitoring Period ¹³
	+ 28 days											
Administrative Procedures												
Informed consent ⁵	X											
Inclusion/Exclusion criteria	X											
Demographics/Medical history	X											
Prior/Concomitant medication	X	X	X	X	X	X	X	X	X	X	X	X
Pembrolizumab (MK-3475) Administration ⁶		X		X		X		X				
NSAIDs & Antiemetic Administration ⁷		X		X		X						
ADXS31-142 Administration ⁸		X		X		X						
Dispense/Prescribe oral prophylactic antibiotics ⁹		X		X		X				X		
Clinical Procedures/Assessments												
Review Adverse events ¹⁰		X	X	X	X	X	X	X	X	X	X	X
Physical examination	X	X		X		X		X		X		
Vital signs ¹¹	X	X		X		X		X		X		
ECOG performance status	X	X		X		X		X		X		
Laboratory Procedures/Assessments: analysis performed by LOCAL laboratory												
CBC with Differential	X	X		X		X		X		X		X
Serum Chemistry Panel	X	X		X		X		X		X		X
PT/INR and aPTT	X											
Urinalysis	X	X		X		X		X		X		
TSH, T3, T4 ¹²		X		X		X		X				

CMP (including CRP, ESR) and Blood Cultures												X
Efficacy Measurements/Correlative Studies												
Tumor Imaging ¹⁴	X							X	X			X

1. Repeating 12-week treatment cycles
2. Baseline tumor evaluation will be performed 28 days prior to first dose.
3. Week 3, Week 6 and Week 9 visits will be performed during Cycle 1 only. After Cycle 1, these visits are not required.
4. Safety follow-up will be conducted via a telephone call 30 days (\pm 5 days) and 90 days for SAE assessment after the last study treatment to confirm the resolution of any ongoing AEs. In addition, [REDACTED] testing every 4 weeks and imaging every 12 weeks (\pm 1 week) should continue for subjects who discontinue treatment for reasons other than progression (Refer to Section 7.1.5.3. Post-Treatment Visits).
5. Prior to conducting screening evaluations. Signing of informed consent does not start the 28 days screening window.
6. Prior to administering any prophylactic medications, place a [REDACTED] Pembrolizumab (MK-3475) is to be administered before ADXS31-142 through a temporary IV with a [REDACTED] wait period between infusions.
7. Subjects will receive premedications at least 30 minutes before each ADXS31-142 infusion.
8. Study treatment may be administered [REDACTED] of each scheduled infusion. However, ADXS31-142 should not be administered less than 2 weeks apart without Sponsor approval.
9. All subjects will receive a 7-day course of oral antibiotic therapy starting 72 hours after each ADXS31-142 infusion. All subjects will also receive an additional 6-month oral antibiotic course to be initiated 72 hours following the last dose of study treatment or upon discontinuation (See Section 7.1.5.3).
10. AEs and SAEs will be assessed from the time Informed Consent through the completion of the *Lm* Surveillance Monitoring period. All AE/SAEs will be followed through resolution. All AEs/SAEs experienced during this period must be recorded on the eCRF.
11. Monitor vital signs (including weight) pre-dose for all infusions. Vital signs will be checked prior to pembrolizumab (MK-3475) administration, prior to the ADXS31-142 infusion and every [REDACTED] for the first [REDACTED] following the completion of the ADXS31-142 infusion. Weight will be collected once at every visit. Height will be measured at screening only.
12. Thyroid function tests will be monitored only during combination therapy.
13. *Lm* Surveillance Monitoring will include routine monitoring of CBC (excluding LDH), CMP (including CRP, ESR) and blood cultures. All testing will be performed every 3 months (\pm 2 weeks) for 3 years beginning 3 months after the subject's last dose of study treatment or at the time of study discontinuation. During the 6-month post-treatment antibiotic period, AEs that occur, which are deemed by the Investigator to be related to *Lm* or antibiotic treatment, along with the concomitant medications used to treat the AE(s) will be recorded on the eCRF.
14. CT/MRI of the abdomen/pelvis and bone scan. Repeat every 10 weeks (\pm 1 week) during the first cycle and every 12 weeks (\pm 1 week) during treatment. Evaluation should continue every 12 weeks (\pm 1 week) for subjects who discontinue treatment for reasons other than progression.
15. [REDACTED]
16. [REDACTED]
17. [REDACTED]
18. [REDACTED]

